#### Unexpected Adverse Event

For FDA reporting purposes, an unexpected AE is an AE not previously reported or an AE that occurs with specificity, severity or frequency that is not consistent with the current investigator's brochure.

### 10.2 Relationship to Investigational Product

The assessment of the relationship of an AE to the administration of the study drug is a clinical decision based on all available information at the time the event is being documented. The following definitions of the relationship between the study drug and the AE (including SAEs) should be considered:

- Unrelated - No possible relationship

The temporal relationship between drug exposure and the adverse event onset/course is unreasonable or incompatible, or a causal relationship to study drug is implausible.

- Unlikely - Not reasonably related, although a causal relationship cannot be ruled out

While the temporal relationship between drug exposure and the adverse event onset/course does not preclude causality, there is a clear alternate cause that is more likely to have caused the adverse event than the study drug.

- Possible - Causal relationship is uncertain

The temporal relationship between drug exposure and the adverse event onset/course is reasonable or unknown, de-challenge or re-challenge information is either unknown or equivocal, and while other potential causes may not exist, a causal relationship to the study drug does not appear probable.

- Probable - High degree of certainty for causal relationship

The temporal relationship between drug exposure and the adverse event onset/course is reasonable. There is a clinically compatible response to de-challenge (re-challenge is not required), and other causes have been eliminated or are unlikely.

- Definite - Causal relationship is certain

The temporal relationship between drug exposure and the adverse event onset/course is reasonable, there is a clinically compatible response to de-challenge, other causes have been eliminated, and the event must be definitive pharmacologically or phenomenologically, using a satisfactory re-challenge procedure if necessary.

### 10.3 Intensity/Severity of an Adverse Event

In addition to assessing the relationship of the administration of the investigational product to AEs, an assessment is required of the intensity (severity) of the event. The following classifications should be used:

- *Mild:*  
A mild AE is an AE, usually transient in nature and generally not interfering with normal activities.
- *Moderate:*  
A moderate AE is an AE that is sufficiently discomforting to interfere with normal activities.
- *Severe:*  
A severe AE is an AE that incapacitates the subject and prevents normal activities. Note that a severe event is not necessarily a serious event. Nor must a serious event necessarily be severe.

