### 5.2.2 Exclusion Criteria

- Motor Neurone Disease syndromes that do not have clinically detectable Upper Motor Neurone signs (e.g., flail arm or flail leg onset of ALS)
- A clinical diagnosis of dementia as determined by the Investigator.
- Current treatment with anticoagulants (e.g., warfarin, novel oral anticoagulants, heparin) that might preclude safe completion of the lumbar puncture.
- Condition that precludes the safe performance of routine lumbar puncture, such as prohibitive lumbar spinal disease, bleeding diathesis, or clinically significant coagulopathy or thrombocytopenia.
- Use of investigational drugs or devices within 60 days prior to baseline (dietary supplements taken outside of a clinical trial are not exclusionary, e.g., coenzyme Q10).

- Prolonged prothrombin time or activated partial thromboplastin time >2xULN
- Severe hypertension or hypotension
- Glomerular filtration rate (GFR) <35 mL/min
- Prior exposure to any exogenous form of APC
- FVC at screening of <50% of predicted
  - *Participants who fail to meet this criterion due to technical difficulties may be considered at the Principal Investigator's discretion.*
- Inability to lie flat for investigational procedures (MRI, PET, Lumbar Puncture)
- Previously obtained MRI scan with evidence of clinically significant neurological disorder (in the opinion of the Investigator).
- Presence of any of the following clinical conditions at the time of screening:
  - Drug or alcohol abuse, unstable medical disease (such as unstable angina or chronic obstructive pulmonary disease), active infectious disease (such as Hepatitis B or C or tuberculosis), current malignancy, unstable psychiatric illness (based on a prior psychiatric diagnosis that is unstable as determined by the subject's treating Psychiatrist) defined as psychosis or untreated major depression within 90 days of the screening visit, or any other condition that, in the opinion of the Investigator, might interfere with study conduct or interpretation of the study results.

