#### 10.4 Recording of Adverse Events

Adverse events including clinically significant biological sample test abnormalities, whether observed by the investigator, elicited from or volunteered by the subject, should be recorded on the Adverse Event Log. This will include a brief description of the experience, the date of onset, the date of resolution, the severity, and seriousness and whether the event was related to participation in the research study.

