## 15.4 Clinical Safety Laboratory data

Clinical safety laboratory data (haematology, biochemistry, and urine chemistry) will be summarised at each protocol scheduled time point, by dose cohort, and overall. Actual values and actual changes from baseline will be presented.

Urinalysis results evaluation (normal, abnormal not clinically significant or abnormal clinically significant) will be summarised at each protocol scheduled time point, by dose cohort with frequency tabulations.

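### Symptom-free laboratory abnormalities can only be graded mild under Section 10.3, and no planned table counts patients with large blood abnormalities independently of investigator judgement

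*Combined protocol and SAP*

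**What the plan says.** Section 10.3 asks for an intensity assessment of every adverse event and states: "The following classifications should be used". Three classes follow. The lowest is worded thus: "A mild AE is an AE, usually transient in nature and generally not interfering with normal activities". The middle class requires enough discomfort to disturb everyday function, and the top class requires that the patient is incapacitated.

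Section 10.4 brings laboratory findings onto the same log: "Adverse events including clinically significant biological sample test abnormalities, whether observed by the investigator, elicited from or volunteered by the subject, should be recorded". Each entry carries a severity. Whether a laboratory result is clinically significant is left to judgement, with no numeric criterion.

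For haematology, biochemistry and urine chemistry, Section 15.4 plans summaries at each scheduled time point: "Actual values and actual changes from baseline will be presented". A tabulation into normal and two kinds of abnormal is planned for urinalysis only. Section 15.1 defines the continuous summary as n, mean, median, SD, minimum and maximum, with a 95% CI where appropriate, and gives categorical data exact Clopper-Pearson intervals. Section 15.2 counts treatment-emergent events, and patients with at least one, by preferred term within system organ class.

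The only numeric coagulation limit in the document is an entry criterion in Section 5.2.2: "Prolonged prothrombin time or activated partial thromboplastin time >2xULN".

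**The concern.** All three severity classes turn on what the patient feels or can do. A prolonged APTT, a low platelet count or a raised transaminase usually causes no symptoms, so the scale cannot distinguish a small change from a large one.

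This matters here for three reasons. Safety is the primary outcome, and Section 3.1 names laboratory testing as one of the ways it is evaluated. Section 1 describes the drug as a variant of a protein with systemic anticoagulant activity, in which that activity is significantly reduced; it does not say the activity is absent. Section 4 says the results are to guide dosing in later chronic studies, so the laboratory record from each dose cohort will be read closely.

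Severity also enters the definition of an unexpected event in Section 10.1, which compares specificity, severity and frequency with the investigator's brochure. A scale that cannot register the size of a laboratory change weakens the severity part of that comparison.

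**Working it through.** The plan gives no figure on this point to reproduce. The cohort size is consistent throughout: 2 cohorts × 8 = 16 patients (Synopsis, Section 2).

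**Step 1: classify a silent laboratory event.** Take an APTT prolongation that the investigator judges clinically significant and that causes no symptoms.

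- Severe requires incapacity: not met.
- Moderate requires discomfort that interferes with activities: not met.
- Mild requires, in general, no interference: met.

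The size of the change appears in none of the three tests. The qualifiers in the mild definition (usually, generally) soften it but open no route to a higher class. The result is mild at any size.

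**Step 2: follow the event through the planned outputs.**

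- AE log and listing: present, graded mild.
- AE table (15.2): counted once by preferred term if treatment-emergent, without magnitude. No table by severity is named.
- Laboratory table (15.4 with 15.1): its value enters the mean, median, SD, minimum and maximum at that time point.
- Count of patients beyond a limit, or shift from baseline: none planned for blood tests.

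An abnormality not judged clinically significant appears only in the laboratory table and is counted nowhere.

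**Step 3: what the laboratory table would show.** Assumption for illustration: one of 8 patients has APTT rise from 30 s to between 60 s and 90 s (2-fold to 3-fold), and the other seven do not change.

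- Mean change, cohort of 8: 30/8 = 3.75 s to 60/8 = 7.5 s.
- Mean change, all 16: 30/16 = 1.875 s to 60/16 = 3.75 s.
- Median change: 0 s.
- Maximum change: +30 s to +60 s.

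For platelets, if one of 8 falls to 1/2 or 1/3 of baseline, the cohort mean relative to baseline is (7 + 0.5)/8 = 0.94 or (7 + 0.333)/8 = 0.92, and the minimum is 0.50 or 0.33.

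The mean and median barely move, but the minimum and maximum reveal the extreme value. They do not say how many patients had one. With one patient at 2-fold the maximum ratio is 2.0; with two patients at 2-fold it is still 2.0, and the median is 1.0 in both cases. Similarly, high maxima on two different days may come from one patient or from two.

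**Step 4: what a count would add.** Clopper-Pearson 95% limits, the method already named in Section 15.1:

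- x = 0: upper limit = 1 − 0.025^(1/n).
- x ≥ 1: lower = Beta quantile (0.025; x, n − x + 1), upper = Beta quantile (0.975; x + 1, n − x).

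| Patients beyond limit | % | 95% CI |
|---|---|---|
| 0/8 | 0 | 0 to 36.9% |
| 1/8 | 12.5 | 0.3% to 52.7% |
| 2/8 | 25.0 | 3.2% to 65.1% |
| 0/16 | 0 | 0 to 20.6% |
| 1/16 | 6.3 | 0.2% to 30.2% |

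The intervals are wide, and reporting them makes plain how little an absence of events in eight patients excludes.

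**The case against.** The strongest reply is that most of the consequences are already handled.

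- A reader might infer that the laboratory tables are mean-based and hide the case. They are not: Section 15.1 includes the median, minimum and maximum, and in Step 3 the table would show +60 s beside a mean of 7.5 s.
- A reader might infer that the event is not counted. If it is judged clinically significant and is treatment-emergent, Section 15.2 counts it by preferred term, as 1/8 in the example.
- A reader might infer that a mild grade keeps an important event from being reported. Section 10.1 lets an important medical event be serious on medical judgement, Section 10.3 itself separates serious from severe, and the 24-hour notice in Section 10.5 depends on seriousness.
- A reader might infer that misgrading makes the comparison of 15 mg with 30 mg look cleaner. No planned table uses severity, and no rule in the document for dosing or for moving between cohorts refers to it, so no such route is documented.
- A reader might infer that the entry limit for PT and APTT is contradicted on treatment. It is stated as an exclusion only. The lumbar puncture condition in Section 7.2.5 rests on clinical significance, the same kind of judgement as Section 10.4.

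All of this stands, and it limits the point. Two things remain: the grade itself carries no information on size for silent laboratory events, and the only planned count of blood abnormalities depends on an investigator judgement without a numeric criterion, in an open-label study.

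**Conclusion.** The concern holds in a limited form. By the plan's own definitions, a symptom-free laboratory abnormality is graded mild at any size. The effect is confined to the AE log, the listings and the severity part of the expectedness judgement. Separately, no planned output gives the number of patients with a large PT, APTT, platelet or biochemistry abnormality independent of investigator judgement.

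The first conclusion rests on the text alone. The sizes in Step 3 rest on assumed values and show only what the tables can and cannot convey; the document gives no basis for expecting changes of that size. The exact intervals depend only on eight patients per cohort and the planned method. This is worth correcting because safety is primary and the correction is cheap, but it does not invalidate the safety analysis.

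**What to change.** In Section 10.3, state that laboratory adverse events are graded on a pre-specified numeric laboratory scale chosen by the sponsor, and keep the three activity-based classes for symptomatic events.

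In Section 15.4, add by dose cohort and overall:

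- the number and percentage of patients with any post-dose PT or APTT above a pre-specified limit; the limit of twice the upper limit of normal used at entry is one option, for reporting only and not as a treatment rule;
- baseline-to-worst post-dose shift tables for platelets, haemoglobin, AST, ALT and creatinine;
- the Clopper-Pearson intervals already planned for categorical data.

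State which pre-dose result serves as baseline for these tables, since Section 6.2.2 spreads the baseline assessments over Days 1 to 3.

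The cost is one paragraph and a small set of derived tables. The blood tests are already scheduled, and Section 7.1.5 provides a central laboratory with consistent normal ranges. The downsides are slightly more grading work and a safety profile that may look less favourable.

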#### 10.4 Recording of Adverse Events

Adverse events including clinically significant biological sample test abnormalities, whether observed by the investigator, elicited from or volunteered by the subject, should be recorded on the Adverse Event Log. This will include a brief description of the experience, the date of onset, the date of resolution, the severity, and seriousness and whether the event was related to participation in the research study.

#### 10.5 Responsibilities for Reporting Serious Adverse Experiences

- The Investigator should notify the sponsor within 24 hours of his/her becoming aware of the occurrence of a serious adverse experience or suspected unexpected serious adverse reaction (SUSAR).
- The following information should be supplied if available at the time of the email or telephone call: subject number, subject age and gender, date of onset of event, event description, whether event required treatment, death and autopsy report, an identification of which criteria for a serious experience have been met, the Investigator's current opinion of the relationship between the event and study participation.
- The Investigator will comply with Macquarie University HREC regulations regarding the reporting of adverse experiences.

### 11. Referrals for Unexpected Results of Study Participation

If a research assessment, lab or MRI result reveals a clinically significant abnormality (e.g., renal impairment on metabolic profile) the subject should be informed of this result and the Investigator should provide the subject with the appropriate referral as necessary.

## 12. Potential Risks

### 12.1 Blood Sampling

Risks associated with venous blood draw include pain and bruising at the site where the blood is taken. Sometimes people can feel lightheaded or even faint after having blood drawn.

### 12.2 Lumbar Puncture

The most common risks of a lumbar puncture are pain at the site and a temporary headache usually due to a small amount of CSF leakage around the needle insertion site. Lying down for a few hours after the test can make a headache less likely to occur. There is a slight risk of infection because the needle breaks the skin's surface, providing a possible portal of entry for bacteria. A temporary numbness to the legs or lower back pain may be experienced. There is a small risk of bleeding in the spinal canal. Subjects will have blood drawn at Screening to test for coagulopathies.

### 12.3 MRI – ALS Protocol

Subjects should notify the study doctor if they suffer from claustrophobia because they may become anxious while in the magnetic resonance scanner. There may be loud noises such as knocking or hammering that occur while the MRI is being conducted. Subjects should also inform the study doctor if they have a pacemaker or metal implants (screws, plates or clips) because this may preclude MR evaluation. The imaging will take 60 minutes.

### 12.4. PET Imaging

Specific potential risks for PET imaging are as follows:

- 1) radiation exposure from [F]FEMPA
- 2) (see companion protocol),
- 3) having an intravenous injection.

### 12.5 Unknown Risks

In addition to the known risks listed above, the imaging procedures in this study may cause unknown risks to the participant, or a developing embryo or fetus or possible risks to the future offspring of male participants. Female subjects or a female partner of a male subject who report a pregnancy within 30 days of [F]FEMPA injection will be asked to have a urine pregnancy test.

## 13. Regulatory / Ethics

### 13.1. Compliance Statement

This study will be conducted in accordance with the Good Clinical Practice (GCP) and the International Conference on Harmonization (ICH) guidelines and any applicable national and local regulations.

All procedures not described in this protocol will be performed according to the study Operation Manuals unless otherwise stated. Laboratory tests/evaluations described in this protocol will be conducted in accordance with quality laboratory standards as described in the central laboratory manual unless otherwise stated.

### 13.2. Informed Consent

In accordance with relevant regulations, an informed consent agreement explaining the procedures and requirements of the study, together with any potential hazards/risks must be read by and explained to each subject. Each subject will sign such an informed consent form. The subject must be assured of the freedom to withdraw from participation in the study at any time.

It is the Investigator's responsibility to make sure that the subject understands what she/he is agreeing to and that written informed consent is obtained before

the subject is involved in any protocol-defined procedures including screening procedures. It is also the Investigator's responsibility to retain the original signed consent form and provide each subject with a copy of the signed consent form.

The Project Management Team must be given an opportunity to review the consent forms prior to site Human Research Ethics Committee (HREC) submission and before it is used in the study.

### **13.2 Human Research Ethics Committee Review**

All necessary information will be supplied by the Investigator including the protocol and consent forms to the HREC for review and approval. The Investigator agrees to provide the HREC all appropriate material. The trial study will not begin until the Investigator has obtained appropriate HREC approval. A copy of the approval letter and approved consent form must be submitted to the CRO.

The Investigator will request from the HREC a composition of the members reviewing the protocol and informed consents. Appropriate reports on the progress of this study by the Investigator will be made to the HREC and the CRO in accordance with institutional and government regulations. The CRO will notify the site when the HREC may be notified of study completion. It is the Investigator's responsibility to notify the HREC when the study ends. This includes study discontinuation, whether it is permanent or temporary. A copy of the site HREC acknowledgement of study completion must be submitted to the Project Management Team.

### **13.3. Protocol Amendments**

Changes to the protocol should only be made via an approved protocol amendment. Protocol amendments must be approved by the study's Steering Committee and the HREC prior to implementation, except when necessary to eliminate hazards and/or to protect the safety, rights or welfare of subjects.

### **13.4 Subject Confidentiality**

The site Investigator must assure that the confidentiality of subjects, including their personal identity and personal medical information, will be maintained at all times. Subjects will be identified by consecutive ID numbers issued by the data management team on case report forms and other study materials submitted to data management, the pathology laboratory, and bio-repository.

After a subject signs an informed consent form, it is required that the site Investigator permit regulatory agency personnel to review the signed informed consent(s) and that portion of the subject's medical record that is directly related to the study. This shall include all study relevant documentation including subject medical history to verify eligibility, laboratory test result reports, admission/discharge summaries for hospital admissions occurring while the subject is in the study, and autopsy reports for deaths occurring during the study (when available).

### 13.5 COVID-19 Contingency Plan

The COVID-19 pandemic and the restrictions imposed by the NSW government present an unprecedented challenge to clinical trials. However, compliance and adherence to these regulations and the recommendations of Macquarie University is a priority in order to maintain the safety of staff and trial participants.

The following protocol modifications will be applied as deemed appropriate by the Principal Investigator in accordance with COVID-19 regulations:

- The exclusion criteria of *forced vital capacity (FVC) at screening of <50% of predicted* will not be assessed as part of eligibility for trial participation.
- The inclusion criteria of:
  - *symptom onset less than 36 months before screening*
  - *diagnosis of ALS less than 24 months before screening*

will be re-assessed by the Principal Investigator in the event that a trial participant's eligibility is affected by delays to their randomization date.

## 14. Documentation

### 14.1 Study File and Source notes

The Investigator shall maintain and retain site documentation consistent with the requirements of the TGA annotated ICH-GCP. Source notes will include all printouts/reports of tests/procedures, as specified in the protocol, for each subject. This documentation, together with the subject's hospital/medical records, and the participant's original signed consent form is the subject's source information for the study.

## 15. Statistical Analysis

### 15.1 Demographic and Baseline Characteristics

Descriptive analyses will be reported for this study. Continuous parameters, will be summarised as the number of observations, mean, median, standard deviation, minimum, maximum, and if appropriate two-sided 95% CI's. Categorical parameters will be summarised as frequencies, percentages, and exact Clopper-Pearson two-sided 95% CI's. Data will be summarised by dose cohort, and overall.

